7.1.7. Additional Analysis of Adverse Events

7.1.7.1. Stage 3 Opportunistic Illnesses in HIV

On an ongoing basis, AEs will be reviewed for events that might meet the definition of stage 3 opportunistic illnesses in HIV that are indicative of an AIDS-defining diagnoses (see Protocol Appendix 5). The Gilead medical monitor will review the possible stage 3 opportunistic illnesses and approve the events that meet the definition. Events that meet the stage 3 opportunistic illness definition of an AIDS-defining diagnosis will be listed.

7.1.7.2. Cardiovascular or Cerebrovascular Events

Preferred terms for defining cardiovascular or cerebrovascular events are from relevant Standardised MedDRA Query (SMQ). The selected PT listing was provided by Gilead PVE and reviewed by Gilead medical monitors (see details in [Appendix 3](#)).

The number and percentage of subjects with treatment-emergent cardiovascular or cerebrovascular events and serious cardiovascular or cerebrovascular events by PT will be provided by treatment group based on the All B/F/TAF Analysis Set. A data listing of cardiovascular or cerebrovascular events will be provided.

7.1.7.3. Hepatic Events

Preferred terms for defining hepatic events are from 15 relevant SMQs, which are identified as non-infectious and non-congenital hepatobiliary disorders. The selected PT listing was provided by Gilead PVE and reviewed by Gilead medical monitors (see details in [Appendix 4](#)).

The number and percentage of subjects with treatment-emergent hepatic events and serious hepatic events by PT will be summarized by treatment group based on the All B/F/TAF Analysis Set. A data listing of hepatic events will be provided.

7.2. Laboratory Evaluations

Laboratory data will be analyzed and summarized using both quantitative and qualitative methods using All B/F/TAF Analysis Set. The analysis will be based on values reported in conventional units. When values are below the LOQ, they will be listed as such, and the imputed value will be used for the purpose of calculating summary statistics as specified in Section 3.7.

A by-subject listing for laboratory test results will be provided by subject ID number and visit in chronological order for hematology, serum chemistry, and urinalysis separately for all data collected from both phases of the study. Values falling outside of the reference range and/or having a severity grade of 1 or higher on the Gilead Grading Scale for Severity of Adverse Events and Laboratory Abnormalities will be flagged in the data listings, as appropriate.

7.2.1. Summaries of Numeric Laboratory Results

Descriptive statistics will be provided by treatment group for each laboratory test specified in the study protocol as follows:

- Baseline values
- Values at each postbaseline analysis window
- Change from baseline at each postbaseline analysis window
- Percentage change from baseline to each postbaseline analysis window (if specified)

A baseline laboratory value will be defined as the last nonmissing value obtained on or prior to the date of first dose of B/F/TAF. Change from baseline to a postbaseline visit will be defined as the postbaseline value minus the baseline value. The mean, median, Q1, Q3, minimum, and maximum values will be displayed to the reported number of digits; SD values will be displayed to the reported number of digits plus 1.

In the case of multiple values in an analysis window, data will be selected for analysis as described in Section 3.8.3.

Calcium Corrected for Albumin

Calcium corrected for albumin will be calculated and summarized for the study. The following formula will be used when both serum calcium and albumin results for a given blood drawn are available and serum albumin value is < 4.0 g/dL.

- Calcium corrected for albumin (mg/dL) = serum calcium (mg/dL) + 0.8 x (4.0 - albumin (g/dL)).

Toxicity grading for calcium will be applied based on the corrected values.

Estimate GFR

The following formulae will be used to calculate eGFR_{CG}:

- eGFR(CG) (mL/min) = [(140 – age (yrs)) × weight (kg) × (0.85 if female)] / (SCr (mg/dL) × 72), where weight is total body mass in kilograms.

7.2.2. Graded Laboratory Values

The Gilead Grading Scale for Severity of Adverse Events and Laboratory Abnormalities will be used for assigning toxicity grades (0 to 4) to laboratory results for analysis. Grade 0 includes all values that do not meet the criteria for an abnormality of at least Grade 1. For laboratory tests with criteria for both increased and decreased levels, analyses for each direction (ie, increased, decreased) will be presented separately.

If there is any laboratory toxicity grading scale overlapping with the normal reference ranges (eg, grade 1 scale overlaps with normal reference ranges), laboratory values that are within the normal range will be grade 0, except for lipid tests.

For triglycerides, LDL, and cholesterol, protocol-specified toxicity grading scale is for fasting test values, so nonfasting lipid results (or lipid results without a known fasting status) will not be graded or summarized by toxicity grades.

For the international normalized ratio (INR) of prothrombin time (PT), protocol-specified toxicity grading scale depends on the upper limit of normal range (ULN). While the ULN of INR depends on whether the subject is taking anticoagulant medication or not (ie, Not taking oral anticoagulant: 0.8 – 1.2; Taking oral anticoagulant: 2.0 – 3.0), this information is not collected by the reference laboratory. As a result, INR will be graded by assuming subject is not taking an oral anticoagulant, which is a conservative approach that may lead to over-reporting of abnormalities for INR. Consequently, INR and PT will not be included in summaries of laboratory abnormalities, but will be included in listings for the following reasons: 1) INR and PT are reflexive tests; 2) only the absolute values, not the toxicity grade, are needed for subject management purposes; and 3) more importantly, the toxicity grades for INR may be over-reported.

7.2.2.1. Treatment Emergent Laboratory Abnormalities

Treatment-emergent laboratory abnormalities are defined as values that increase at least 1 toxicity grade from baseline at any postbaseline time point, up to 30 days from the last dose date of B/F/TAF. If the relevant baseline laboratory value is missing, any abnormality of at least Grade 1 observed within the time frame specified above will be considered treatment-emergent.

Fasting glucose and nonfasting glucose (including glucose results without a known fasting status) are graded based on different grading scales as specified in the protocol.

Treatment-emergent laboratory abnormalities will be summarized for fasting glucose. Maximum postbaseline grade, instead of treatment-emergent grade, for nonfasting glucose (including glucose results without a known fasting status) will be summarized, as nonfasting glucose was not assessed at baseline visit for most of the subjects; therefore, an abnormality is treatment-emergent or not cannot be determined for these subjects.

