### **6.2. Pretreatment Assessments**

#### **6.2.1. Screening Visit**

Subjects will be screened within 30 days before Day 1 to determine eligibility for participation in the study. The screening visit may coincide with the Week 48 OLE visit or any post-Week 48 OLE visits in study GS-US-236-0128 or the Week 96 visit or any post-Week 96 visits in study GS-US-292-0109, or may be conducted after completion of the Week 144 visit or any post Week 144 visits for studies GS-US-292-0104 or GS-US-292-0111. The following will be performed and documented at screening:

- Obtain written informed consent
- Obtain medical history including history of HIV-1 disease-related events and prior medications within 30 days of the screening visit
- Complete physical examination (urogenital/anorectal exams will be performed at the discretion of the Investigator)
- 12-lead ECG performed supine
- Height
- Vital signs measurement (blood pressure, pulse, respiration rate, and temperature), including weight
- Urine collection for the following laboratory procedures:
  - Urinalysis

- Blood sample collection for the following laboratory analyses:
  - Serum pregnancy test (women of childbearing potential only). If the test is positive, the subject will not be enrolled
  - FSH test is required for women who have stopped menstruating for  $\geq$  12 months but do not have documentation of ovarian hormonal failure
  - Chemistry profile: alkaline phosphatase, AST, ALT, GGT, total bilirubin, direct and indirect bilirubin, total protein, albumin, bicarbonate, BUN, calcium, chloride, creatinine, glucose, phosphorus, magnesium, potassium, sodium, uric acid, amylase (reflex lipase testing is performed in subjects with total amylase  $> 1.5 \times$  ULN), and TSH
  - Estimated glomerular filtration rate according to the Cockcroft-Gault formula:

$$\frac{(140 - \text{age in years}) \times (\text{wt in kg})}{72 \times (\text{serum creatinine in mg/dL})} \times 0.85 = \text{CrCL (mL/min)}$$

$$\frac{(140 - \text{age in years}) \times (\text{wt in kg}) \times 0.85}{72 \times (\text{serum creatinine in } \mu\text{mol/L}) \times 0.6786} = \text{CrCL (mL/sec)}$$

- Hematology profile: complete blood count (CBC) with differential and platelet count
- CD4+ cell count
- Plasma HIV-1 RNA
- Hepatitis B Virus (HBV) blood panel: Hepatitis B virus surface antigen (HBsAg), Hepatitis B virus surface antibody (HBsAb) and Hepatitis B virus core antibody (HBcAb)

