### 6.4. Treatment Assessments (Weeks 4-48)

The following evaluations are to be completed at the end of Weeks 4, 8, 12, 24, 36, and 48 unless otherwise specified.

Study visits are to be completed within  $\pm$  2 days of the protocol-specified visit date based on the Day 1 visit through Week 12 and completed within  $\pm$  6 days at Week 24 and Week 36, unless otherwise specified. The visit window at Week 48 will be  $\pm$  6 weeks of the protocol-specified visit date, and these clinical visit windows coincide with the Week 48 statistical analysis window for HIV-1 RNA.

Regularly scheduled evaluations will be made on all subjects whether or not they continue to receive study drug.

- Review of AEs and changes in concomitant medications
- Complete physical examination (**Weeks 24 and 48**) (urogenital/anorectal exams will be performed at the discretion of the Investigator) or symptom-directed physical examination as needed
- Vital signs measurement (blood pressure, pulse, respiration rate, and temperature), including weight
- 12-lead ECG performed supine (**Weeks 24 and 48**)
- Urine collection for the following laboratory procedures:
  - Urinalysis
  - Urine albumin, urine creatinine, urine protein, retinol binding protein and beta-2 microglobulin (**Weeks 24 and 48**)
  - Urine pregnancy test (females of childbearing potential only); positive urine pregnancy tests will be confirmed with a serum test. If the test is positive, subjects on GS-9883/F/TAF will be discontinued.
  - Urine storage sample for possible additional clinical testing

- Blood sample collection for the following laboratory analyses:
  - Chemistry profile: alkaline phosphatase, AST, ALT, GGT, total bilirubin, direct and indirect bilirubin, total protein, albumin, bicarbonate, BUN, calcium, chloride, creatinine, glucose, phosphorus, magnesium, potassium, sodium, uric acid, and amylase (reflex lipase testing is performed in subjects with total amylase  $> 1.5 \times$  ULN). At Weeks 12, 24 and 48, analyses of glucose will be done as part of the fasting metabolic assessments and not as part of the chemistry profile. At Weeks 24 and 48, TSH will also be analyzed.

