3.8.1. Definitions

Study Day 1 is defined as the day when the first dose of B/F/TAF (either in the randomized phase or extension phase) was taken. For subjects randomized to the B/F/TAF group, the first dose date is the same as the randomized phase first dose date. For subjects randomized to the SBR group, the first dose date is defined as the earliest nonmissing start date of B/F/TAF recorded on the Study Drug Administration eCRF.

Study Days are calculated relative to Study Day 1 for the all B/F/TAF analysis. For events that occur on or after the Study Day 1 date, study days are calculated as (visit date minus date of the first dose plus 1). For events that occur prior to Study Day 1, study days are calculated as (visit date minus date of the first dose).

Last Dose Date is defined as the maximum, nonmissing end date of B/F/TAF, recorded on the Study Drug Administration eCRF form with “Study Drug Permanently Discontinued” box checked for subjects who prematurely discontinued study drug or who completed study drug according to the Study Drug Completion eCRF.

If the date of last dose is missing (eg, due to lost to follow-up) for subjects who prematurely discontinued study drug, the maximum of nonmissing study drug start dates and end dates, the clinical visit dates, and the laboratory visit dates excluding the date of 30-day follow-up visit will be used to impute the last dose date.

Last Study Date is the maximum of nonmissing study drug start dates and end dates, the clinic visit dates, and the laboratory visit dates, including the 30-day follow-up visit date for subjects who prematurely discontinued or completed the study according to the Study Completion eCRF.

Baseline value is defined as the last nonmissing value obtained on or prior to the Study Day 1 for all assessments.

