- ii) For glucose grading, as specified in SAP Section 7.2.2.1, the treatment-emergent flag cannot be determined for nonfasting glucose (including glucose results without a known fasting status). As a result, these records will be excluded from the “Maximum Treatment-emergent Toxicity Grade” summary in the “Treatment-emergent Laboratory Abnormalities” or “Treatment-emergent Grade 3 or 4 Laboratory Abnormalities” summary tables. In addition, fasting glucose and non-fasting glucose will be listed as two separate laboratory tests in the “Laboratory Abnormalities” and “Grade 3 or 4 Laboratory Abnormalities” listings. Only a maximum postbaseline toxicity flag will be displayed and the treatment-emergent flag will not be displayed for nonfasting glucose as the treatment-emergent flag cannot be determined for nonfasting glucose.

8) Graded Laboratory Abnormalities Summary

The following labels will be used for treatment-emergent laboratory abnormalities and treatment-emergent Grade 3 or 4 laboratory abnormalities summary tables and listings:

Battery	Lab Test Label Used in l-labtox Listing	Toxicity Direction	Lab Test Label Used in t-labtox Table
Hematology	Hemoglobin	Decrease	Hemoglobin (Decreased)
	Neutrophils	Decrease	Neutrophils (Decreased)
	Platelets	Decrease	Platelets (Decreased)
	WBC	Decrease	WBC (Decreased)
Chemistry	Albumin	Decrease	Albumin (Decreased)
	Alkaline Phosphatase	Increase	Alkaline Phosphatase (Increased)
	ALT	Increase	ALT (Increased)
	Amylase	Increase	Amylase (Increased)
	AST	Increase	AST (Increased)
	Bicarbonate	Decrease	Bicarbonate (Decreased)
	Corrected Calcium	Increase	Corrected Calcium (Hypercalcemia)
	Corrected Calcium	Decrease	Corrected Calcium (Hypocalcemia)
	Creatine Kinase (CK)	Increase	Creatine Kinase (Increased)
	Creatinine	Increase	Creatinine (Increased)
	GGT	Increase	GGT (Increased)
Lipase	Increase	Lipase (Increased)	
	Magnesium	Decrease	Magnesium (Hypomagnesemia)

Battery	Lab Test Label Used in l-labtox Listing	Toxicity Direction	Lab Test Label Used in t-labtox Table
	Phosphate	Decrease	Phosphate (Hypophosphatemia)
	Serum Glucose (Fasting)	Increase	Serum Glucose (Fasting, Hyperglycemia)
	Serum Glucose (Fasting)	Decrease	Serum Glucose (Fasting, Hypoglycemia)
	Serum Glucose (Nonfasting)	Increase	Serum Glucose (Nonfasting, Hyperglycemia)
	Serum Glucose (Nonfasting)	Decrease	Serum Glucose (Nonfasting, Hypoglycemia)
	Serum Potassium	Increase	Serum Potassium (Hyperkalemia)
	Serum Potassium	Decrease	Serum Potassium (Hypokalemia)

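### Nonfasting glucose: the SAP says treatment emergence cannot be determined, but its own baseline definition admits the Screening (or pre-switch) glucose

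*SAP*

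**What the plan says.** SAP Section 7.2.2.1 grades fasting and nonfasting glucose on separate scales and puts results of unknown fasting status with the nonfasting ones. Fasting glucose gets the usual treatment-emergent summary. For the other group the SAP substitutes "Maximum postbaseline grade, instead of treatment-emergent grade, for nonfasting glucose", and gives the reason: "as nonfasting glucose was not assessed at baseline visit for most of the subjects". Appendix 5 item 7(ii) carries this into programming, stating that "the treatment-emergent flag cannot be determined for nonfasting glucose". These records are left out of the treatment-emergent maximum-grade summary and carry only a maximum-postbaseline flag.

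The baseline rule is stated twice and is not tied to a visit. SAP Section 3.8.1: "Baseline value is defined as the last nonmissing value obtained on or prior to the Study Day 1 for all assessments". SAP Section 7.2.1: "A baseline laboratory value will be defined as the last nonmissing value obtained on or prior to the date of first dose of B/F/TAF".

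In the protocol, the Screening chemistry profile (Section 6.2.1) runs "chloride, creatinine, glucose, phosphorus, magnesium, potassium, sodium, uric acid, amylase", so it includes glucose, and no fasting instruction is given. At Day 1 (Section 6.2.2) glucose is dropped from the chemistry profile and drawn fasting. At Weeks 12, 24 and 48 (Section 6.4), "analyses of glucose will be done as part of the fasting metabolic assessments and not as part of the chemistry profile"; glucose at Weeks 4, 8 and 36 therefore stays in the chemistry profile.

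**The concern.** The stated reason concerns one visit, while the SAP's baseline is any qualifying value up to the first B/F/TAF dose. A glucose not recorded as fasted is scheduled before that dose in both subject groups, so the claim that emergence cannot be determined looks too broad.

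Two things are at stake in the metabolic safety tables. A woman whose nonfasting grade was already present before B/F/TAF is counted at that grade in the postbaseline row. A woman whose nonfasting grade truly rises on B/F/TAF is never flagged as treatment-emergent for that result.

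There is also a consistency problem. Protocol Section 8.6.3 defines treatment-emergent laboratory abnormalities with no exception for nonfasting glucose and treats any graded result as emergent when baseline is missing. SAP Section 7.2.2.1 repeats that default for laboratory tests in general. SAP Section 7.8 then says no change from the protocol's safety analyses is planned.

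**Working it through.** The plan states no figure on this point, so there is none to reproduce. The check sets the schedule against the baseline rule, then traces example values.

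**1. Is a pre-dose value scheduled?**

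- *B/F/TAF group.* Screening falls within 30 days before Day 1 and includes chemistry-profile glucose. Footnote j of protocol Appendix 2 does not list Screening among the visits where glucose moves to the fasting panel. Unless recorded as fasted, the result is nonfasting under SAP Section 7.2.2.1 and meets the definition in SAP Section 3.8.1.
- *SBR to B/F/TAF group.* First B/F/TAF comes in the extension, after the Week 48 visit's fasting draw. The last chemistry-profile glucose before the switch is normally Week 36, preceded by Weeks 8 and 4.

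**2. How many scheduled draws are affected?** By the text of protocol Section 6.4, three of the six postbaseline visits to Week 48 (Weeks 4, 8 and 36) are nonfasting. Footnote j omits Week 12 from the fasting visits, so the protocol is not consistent on whether the count is three or four.

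**3. Rule trace.** Inputs are the nonfasting hyperglycemia grades in protocol Appendix 4: Grade 1, 116 to 160 mg/dL; Grade 2, above 160 to 250; Grade 3, above 250 to 500; Grade 4, above 500. A result is treatment-emergent if the postbaseline grade exceeds the baseline grade.

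| Pre-dose to postbaseline (mg/dL) | Grades | SAP row shows | Treatment-emergent against pre-dose value | Missing-baseline default |
|---|---|---|---|---|
| 100 to 180 | 0 to 2 | 2 | 2 | 2 |
| 140 to 140 | 1 to 1 | 1 | none | 1 |
| 180 to 180 | 2 to 2 | 2 | none | 2 |
| 180 to 140 | 2 to 1 | 1 | none | 1 |
| 180 to 270 | 2 to 3 | 3 | 3 | 3 |
| 270 to 270 | 3 to 3 | 3 | none | 3 |

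True rises get the same grade either way, but under the SAP they carry no treatment-emergent flag. Unchanged or improved values appear in the SAP row and would drop out of a treatment-emergent one. The SAP row always shows the grade that the missing-baseline default would give, as if no woman had a pre-dose value.

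**4. Size.** The documents give no prevalence of pre-existing nonfasting hyperglycemia, so this is an assumed range, applied to the planned 235 women randomized to B/F/TAF:

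- 2%: 235 × 0.02 = 4.7, about 5 women
- 5%: 235 × 0.05 = 11.75, about 12 women
- 10%: 235 × 0.10 = 23.5, about 24 women

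These would be in the row with a stable grade that is not treatment-emergent. Switching SBR women add to the denominator; the documents do not say how many.

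**The case against.** The best defence is that the SAP's sentence is accurate. It speaks of the baseline visit and of most subjects, and Day 1 glucose is indeed fasting. That stands. The fault is in the inference, because the SAP does not define baseline by visit.

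A reader might infer that pre-existing hyperglycemia is being passed off as drug-induced. The documents do not support that. The summary is called maximum postbaseline grade, the treatment-emergent flag is withheld, fasting and nonfasting glucose are listed as separate tests, and the by-subject listings cover both phases, so a high pre-drug value can be seen. Nor does new hyperglycemia vanish: every graded value up to 30 days after last dose counts toward the row. What is lost is the ability to tell new from old.

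A reader might also infer that nearly every woman has a usable nonfasting baseline. That is unproven. Protocol Section 6.2.1 does not state fasting status at Screening and lets that visit coincide with a parent-study visit for some women. A sample recorded as fasted is graded on the other scale and gives no nonfasting baseline.

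Nor can a fold inflation be quoted. With assumed diabetes prevalence, means and variances and no drug effect, simulated ratios of maximum-postbaseline to treatment-emergent Grade 2 or higher run from under 2 to 4 or more, depending on variances that the documents do not give.

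Finally, a grade shift between single draws of unknown prandial state is noisy, and declining to call it treatment-emergent could be defended on that ground. But the SAP does not give that reason, and noise does not make emergence impossible to determine. It is a reason for a footnote.

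The consequence is limited: the final analysis is descriptive and covers B/F/TAF only, no between-arm comparison is affected, and fasting glucose keeps its full treatment-emergent analysis.

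**Conclusion.** The point holds as an inconsistency between a special rule and the SAP's general baseline definition. Wherever a pre-dose glucose not recorded as fasted exists, treatment emergence can be determined under SAP Sections 3.8.1 and 7.2.1, so the blanket statement in Section 7.2.2.1 and Appendix 5 item 7(ii) is wrong for those women. The result is a safety row that does not net out pre-existing hyperglycemia and cannot identify true nonfasting rises as emergent.

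On the assumed prevalences the excess is about 5 to 24 women per 235. That range assumes a grade stable from before to after first dose and a usable pre-dose value in each such woman. The correction is worth making because it is cheap and the rule as written is illogical; it has no bearing on the efficacy conclusion.

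**What to change.** In SAP Section 7.2.2.1 and Appendix 5 item 7(ii):

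- Define the nonfasting baseline as the last nonfasting or unknown-status glucose on or before the first B/F/TAF dose: normally Screening for the B/F/TAF group and Week 36 for SBR to B/F/TAF.
- Derive treatment-emergent grade against it wherever it exists. Keep the maximum-postbaseline rule only for women without one, report how many there are, and footnote the row.
- Footnote that these are single draws of unknown prandial state. A baseline-by-maximum-postbaseline shift table can accompany the row.
- Say which table the row belongs in. Appendix 5 item 8 lists nonfasting glucose labels for the treatment-emergent tables, while item 7(ii) excludes the records from the treatment-emergent maximum.
- If the present rule is kept, record it in SAP Section 7.8 as a departure from protocol Section 8.6.3.

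The cost is SAP wording and one derived flag, with no new data. Under SAP Section 1, a change made after finalization is documented in the clinical study report. The drawback is that some grade shifts will reflect meal timing and not drug, which the footnote and shift table make visible.
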